6.6.1.2 Dose Modification and Toxicity Management of Infusion-Reactions Related to Pembrolizumab

Pembrolizumab may cause severe or life-threatening infusion-reactions including severe hypersensitivity or anaphylaxis. Signs and symptoms usually develop during or shortly after drug infusion and generally resolve completely within 24 hours of completion of infusion. Dose modification and toxicity management guidelines on pembrolizumab associated infusion reaction are provided in [Table 4](#).

Table 4 Pembrolizumab Infusion Reaction Dose Modification and Treatment Guidelines

NCI CTCAE Grade	Treatment	Premedication at Subsequent Dosing
Grade 1 Mild reaction; infusion interruption not indicated; intervention not indicated	Increase monitoring of vital signs as medically indicated until the participant is deemed medically stable in the opinion of the investigator.	None
Grade 2 Requires therapy or infusion interruption but responds promptly to symptomatic treatment (eg, antihistamines, NSAIDs, narcotics, IV fluids); prophylactic medications indicated for ≤ 24 h	
Stop Infusion.
 
Additional appropriate medical therapy may include but is not limited to:
 
 - IV fluids - Antihistamines - NSAIDs - Acetaminophen - Narcotics 
Increase monitoring of vital signs as medically indicated until the participant is deemed medically stable in the opinion of the investigator.
 
If symptoms resolve within 1 hour of stopping drug infusion, the infusion may be restarted at 50% of the original infusion rate (eg, from 100 mL/h to 50 mL/h). Otherwise dosing will be held until symptoms resolve and the participant should be premedicated for the next scheduled dose.
 
Participants who develop Grade 2 toxicity despite adequate premedication should be permanently discontinued from further study drug treatment
	
Participant may be premedicated 1.5 h (\pm 30 minutes) prior to infusion of pembrolizumab with:
 
 - Diphenhydramine 50 mg PO (or equivalent dose of antihistamine). - Acetaminophen 500-1000 mg PO (or equivalent dose of analgesic).

NCI CTCAE Grade	Treatment	Premedication at Subsequent Dosing
Grades 3 or 4 Grade 3: Prolonged (ie, not rapidly responsive to symptomatic medication and/or brief interruption of infusion); recurrence of symptoms following initial improvement; hospitalization indicated for other clinical sequelae (eg, renal impairment, pulmonary infiltrates) Grade 4: Life-threatening; pressor or ventilatory support indicated	
Stop Infusion.
 
Additional appropriate medical therapy may include but is not limited to:
 
 - Epinephrine** - IV fluids - Antihistamines - NSAIDs - Acetaminophen - Narcotics - Oxygen - Pressors - Corticosteroids 
Increase monitoring of vital signs as medically indicated until the participant is deemed medically stable in the opinion of the investigator. Hospitalization may be indicated.
 
**In cases of anaphylaxis, epinephrine should be used immediately.
 
Participant is permanently discontinued from further study drug treatment.
	No subsequent dosing

Abbreviations: CTCAE=Common Terminology Criteria for Adverse Events; IV=intravenous; NCI=National Cancer Institute; NSAIDs=nonsteroidal anti-inflammatory drugs; PO=by mouth.

Appropriate resuscitation equipment should be available at the bedside and a physician readily available during the period of drug administration.

For further information, please refer to the CTCAE v4.0 at <http://ctep.cancer.gov>

6.6.1.3 Other Allowed Dose Interruption for Pembrolizumab

Pembrolizumab may be interrupted for situations other than treatment-related AEs such as medical/surgical events and/or unforeseen circumstances not related to study intervention. However, study intervention is to be restarted within 3 weeks of the originally scheduled dose and within 42 days of the previously administered dose, unless otherwise discussed with the Sponsor. The reason for interruption should be documented in the participant's study record. Imaging should not be delayed for delays in cycle treatment.

6.6.2 Lenvatinib

Lenvatinib dose reduction and interruption for participants who experience lenvatinib- or lenvatinib-pembrolizumab combination therapy-related toxicity will be in accordance with the dose modification guidelines described in [Table 5](#). An interruption of study treatment for more than 28 days will require Sponsor approval before treatment can be resumed.

The starting dose of lenvatinib is 20 mg/day for participants enrolled in the combination therapy arm (Arm 1). Lenvatinib dose reductions for Arm 1 occur in succession based on the previous dose level (14, 10, and 8 mg/day). Any dose reduction below 8 mg/day must be discussed with the Sponsor.

The starting dose of lenvatinib is 24 mg/day for participants enrolled in the monotherapy arm (Arm 2). Lenvatinib dose reductions for Arm 2 will take place in succession based on the previous dose level (20, 14, and 10 mg/day). Any dose reduction below 10 mg/day must be discussed with the Sponsor.

For both Arm 1 and Arm 2, once the lenvatinib dose has been reduced, it may not be increased at a later date, unless the dose has been mistakenly decreased; in this situation, the Sponsor's approval is required to increase the dose.

Refer to the subsections below for management of hypertension (Section 6.6.2.1), proteinuria (Section 6.6.2.2), diarrhea (Section 6.6.2.3), hepatotoxicity (Section 6.6.2.4), thromboembolic events (Section 6.6.2.5), posterior reversible encephalopathy syndrome/reversible posterior leukoencephalopathy syndrome (PRES/RPLS; Section 6.6.2.6), hypocalcemia (Section 6.6.2.7), hemorrhage (Section 6.6.2.8), gastrointestinal perforation or fistula formation (Section 6.6.2.9), QT prolongation (Section 6.6.2.10), and osteonecrosis of the jaw (Section 6.6.2.11) as appropriate, before consulting the dose modification table ([Table 5](#)). For overlapping toxicities of pembrolizumab and lenvatinib, please refer to Section 6.6.3.

See Section 10.7 (Appendix 7) for country-specific requirements.

Table 5 Dose Modification Guidelines for Lenvatinib-Related Adverse Events

Treatment-Related Toxicity ^{a,b}	Management	Dose Adjustment
Grade 1 or Tolerable Grade 2		
	Continue treatment	No change
Intolerable Grade 2^{c,d} or Grade 3^{e,f}		
First occurrence	Interrupt lenvatinib until resolved to Grade 0-1, or tolerable Grade 2	Arm 1: Reduce lenvatinib dose from 20 mg QD to 14 mg QD (1-level reduction) Arm 2: Reduce lenvatinib dose from 24 mg QD to 20 mg QD (1-level reduction)
Second occurrence (same toxicity or new toxicity)	Interrupt lenvatinib until resolved to Grade 0-1, or tolerable Grade 2	Arm 1: Reduce lenvatinib dose from 14 mg QD to 10 mg QD (1-level reduction) Arm 2: Reduce lenvatinib dose from 20 mg QD to 14 mg QD (1-level reduction)
Third occurrence (same toxicity or new toxicity)	Interrupt lenvatinib until resolved to Grade 0-1, or tolerable Grade 2	Arm 1: Reduce lenvatinib dose from 10 mg QD to 8 mg QD (1-level reduction) Arm 2: Reduce lenvatinib dose from 14 mg QD to 10 mg QD (1-level reduction)
Fourth occurrence (same toxicity or new toxicity)	Interrupt lenvatinib	Discuss with Sponsor
Grade 4^g: Discontinue Study Treatment		

Abbreviations: AE=adverse event; BMI=body mass index; CTCAE=Common Terminology Criteria for Adverse Events; QD=once daily.

Note: For grading see CTCAE version 4.0. Collect all AE grades (ie, decreasing and increasing CTCAE grade).

- a. An interruption of study treatment for more than 28 days will require Sponsor's approval before treatment can be resumed.
- b. Initiate optimal medical management for nausea, vomiting, hypertension, hypothyroidism and/or diarrhea prior to any lenvatinib interruption or dose reduction.
- c. Applicable only to Grade 2 toxicities judged by the participant and/or physician to be intolerable.
- d. Obese participants (BMI ≥ 30) with weight loss do not need to return to the baseline weight or within 10% of their baseline weight (ie, Grade 1 weight loss). These participants may restart study intervention at a lower dose once their weight remains stable for at least 1 week and they reach at least a BMI of 25. The new stable weight should be used as the new baseline for further dose reductions.
- e. For asymptomatic laboratory abnormalities, such as Grade ≥ 3 elevations of amylase and lipase that are not considered clinically relevant by the investigator, continuation of treatment should be discussed with Sponsor.
- f. For Grade 3 thromboembolic event, permanently discontinue lenvatinib. See Section 6.6.2.5.
- g. Excluding laboratory abnormalities judged to be non-life-threatening, in which case manage as Grade 3.

6.6.2.1 Management of Hypertension

Hypertension is a recognized side effect of treatment with drugs inhibiting VEGF signaling. Investigators should therefore ensure that participants enrolled to receive treatment with lenvatinib have BP of $\leq 150/90$ mm Hg at the time of study entry and, if known to be hypertensive, have been on a stable dose of antihypertensive therapy for at least 1 week before C1D1. Early detection and effective management of hypertension are important to minimize the need for lenvatinib dose interruptions and reductions.

Regular assessment of BP should be as detailed in the SoA (Section 1.3). Hypertension will be graded using NCI CTCAE v4.0, based on BP measurements only (and not on the number of antihypertensive medications).

If the participant's initial BP measurement is elevated (ie, systolic BP ≥ 140 mm Hg or diastolic BP ≥ 90 mm Hg), the BP measurement should be repeated at least 5 minutes later. One BP assessment is defined as the mean value of 2 measurements at least 5 minutes apart. If the BP assessment (ie, the mean of the 2 BP measurements obtained at least 5 minutes apart) is elevated (systolic BP ≥ 140 mm Hg or diastolic BP ≥ 90 mm Hg), a confirmatory assessment should be obtained at least 30 minutes later by performing 2 measurements (at least 5 minutes apart) to yield a mean value.

Antihypertensive agents should be started as soon as elevated BP (systolic BP ≥ 140 mm Hg or diastolic BP ≥ 90 mm Hg) is confirmed on 2 assessments at least 30 minutes apart. The choice of antihypertensive treatment should be individualized to the participant's clinical circumstances and follow standard medical practice. For previously normotensive participants, appropriate antihypertensive therapy should be started when systolic BP ≥ 140 mm Hg or diastolic BP ≥ 90 mm Hg is first observed on 2 assessments at least 30 minutes apart. For those participants already on antihypertensive medication, treatment modification may be necessary if hypertension persists.

Lenvatinib should be withheld in any instance where a participant is at imminent risk to develop a hypertensive crisis or has significant risk factors for severe complications of uncontrolled hypertension (eg, BP $\geq 160/100$ mm Hg, significant risk factors for cardiac disease, intracerebral hemorrhage, or other significant comorbidities). Once the participant has been on the same antihypertensive medications for at least 48 hours and the BP is controlled, lenvatinib should be resumed as described below.

Participants who have had systolic BP ≥ 160 mm Hg or diastolic BP ≥ 100 mm Hg must have their BP monitored on Day 15 (or more frequently as clinically indicated) until systolic BP has been ≤ 150 mm Hg and diastolic BP has been ≤ 95 mm Hg for 2 consecutive treatment cycles. If a repeat event of systolic BP ≥ 160 mm Hg or diastolic BP ≥ 100 mm Hg occurs, the participant must resume the Day 15 evaluation until systolic BP has been ≤ 150 mm Hg and diastolic BP has been ≤ 95 mm Hg for 2 consecutive treatment cycles.

The following guidelines should be followed for the management of systolic BP ≥ 160 mm Hg or diastolic BP ≥ 100 mm Hg confirmed on 2 BP assessments at least 30 minutes apart:

1. Continue study drug and institute antihypertensive therapy for participants not already receiving this.
2. For those participants already on antihypertensive medication, the dose of the current agent may be increased, if appropriate, or 1 or more agents of a different class of antihypertensive should be added. Study treatment can be continued without dose modification.
3. If systolic BP ≥ 160 mm Hg or diastolic BP ≥ 100 mm Hg persists despite maximal antihypertensive therapy, then lenvatinib administration should be interrupted and restarted at 1 dose level reduction only when systolic BP ≤ 150 mm Hg and diastolic BP ≤ 95 mm Hg and the participant has been on a stable dose of antihypertensive medication for at least 48 hours.
 - If systolic BP ≥ 160 mm Hg or diastolic BP ≥ 100 mm Hg recurs on the first dose reduction despite optimal management of hypertension with antihypertensive medications (either by dose increase or the addition of a different class of antihypertensive), then lenvatinib administration should be interrupted and restarted at an additional dose reduction only when systolic BP ≤ 150 mm Hg and diastolic BP ≤ 95 mm Hg and the participant has been on a stable dose of antihypertensive medication for at least 48 hours.
 - If systolic BP ≥ 160 mm Hg or diastolic BP ≥ 100 mm Hg recurs on the second dose reduction despite optimal management of hypertension with antihypertensive medications (either by dose increase or the addition of a different class of antihypertensive), then lenvatinib administration should be interrupted and restarted at a third dose reduction only when systolic BP ≤ 150 mm Hg and diastolic BP ≤ 95 mm Hg and the participant has been on a stable dose of antihypertensive medication for at least 48 hours.
 - Additional dose reduction should be discussed with Sponsor.

The following guidelines should be followed for the management of Grade 4 hypertension (life-threatening consequences):

1. Institute appropriate medical management
2. Discontinue study drug

See Section 10.7 (Appendix 7) for country-specific requirements.

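### Section 6.6.2.1 names BP ≥160/100 mm Hg as an example for withholding lenvatinib, yet step 1 says to continue at the same confirmed reading, and neither text says which governs

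*Combined protocol and SAP*

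**What the plan says.** All the main text is in Section 6.6.2.1 of the combined protocol and SAP.

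- **Withhold paragraph.** "Lenvatinib should be withheld in any instance where a participant is at imminent risk to develop a hypertensive crisis or has significant risk factors". The risk factors meant are those for serious harm from hypertension that is not under control. The bracketed examples, joined by 'or', start with BP ≥160/100 mm Hg and go on to cardiac risk, intracerebral hemorrhage and other comorbidity. After at least 48 hours on unchanged antihypertensives, and once "the BP is controlled, lenvatinib should be resumed as described below".
- **Numbered steps**, for systolic ≥160 or diastolic ≥100 mm Hg confirmed on two assessments. Step 1: "Continue study drug and institute antihypertensive therapy for participants not already receiving this". Step 2, for those already treated: raise the dose or add an agent; "Study treatment can be continued without dose modification". Step 3: if the pressure "persists despite maximal antihypertensive therapy, then lenvatinib administration should be interrupted and restarted at 1 dose level reduction only when" systolic is ≤150 and diastolic ≤95 mm Hg, with 48 hours of stable medication. The sub-bullets add a second and a third reduction for recurrence.
- **Surrounding text.** "Antihypertensive agents should be started as soon as elevated BP" (systolic ≥140 or diastolic ≥90 mm Hg) is confirmed. The stated aim is: "Early detection and effective management of hypertension are important to minimize the need for lenvatinib dose interruptions and reductions". Footnote b of Table 5 (Section 6.6.2) says: "Initiate optimal medical management for nausea, vomiting, hypertension, hypothyroidism and/or diarrhea prior to any lenvatinib interruption or dose reduction".

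**The concern.** Take a participant on no antihypertensive, with a confirmed reading at or above 160/100 mm Hg, no imminent crisis and no other listed risk factor. On its wording, the withhold paragraph covers this participant through its first example, and step 1 covers the same participant with the opposite instruction. An investigator could cite the section for either action.

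The error could run both ways. A participant whom the sponsor meant to keep on drug may lose doses, and one whom the sponsor meant to withhold may be kept on drug under step 1. After a withhold, one site may resume at the same dose and another one level lower. Section 6.6.2 bars raising a reduced dose again unless the reduction was a mistake, and then only with Sponsor approval.

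Hypertension is a recognized effect of this drug class (Section 6.6.2.1), and safety and tolerability are primary objectives (Section 3). The stake is consistent safety dosing across sites. Uneven practice would also carry into the descriptive summaries of dose modification (Section 9.6.2) and exposure (Section 9.12).

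**Working it through.** The plan gives no figure to reproduce here. The check is a comparison of texts, followed by simple dose arithmetic.

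**1. Same reading, two instructions**

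| Participant with confirmed BP ≥160/100 mm Hg, no crisis, no other risk factor | Withhold paragraph | Numbered steps |
|---|---|---|
| Not on antihypertensives | Withhold (first example) | Step 1: continue |
| On antihypertensives, maximal therapy not yet failed | Withhold (first example) | Step 2: may continue |
| Persists despite maximal therapy | Withhold | Step 3: interrupt, restart one level lower |

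The first row is a direct conflict. The second is softer, because step 2 permits continuing but does not order it. The third agrees. The steps carry no exception for participants under the withhold paragraph, and that paragraph does not claim precedence.

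The triggers also differ in form: 160/100 in the paragraph, systolic 'or' diastolic in the steps. A reading of 165/95 mm Hg meets the steps but may or may not meet the paragraph.

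**2. Can the first row occur?** Yes. Inclusion criterion 13 (Section 5.1) admits BP up to 150/90 mm Hg with or without antihypertensives. Treatment starts at a confirmed ≥140 or ≥90, so some participants will already be treated before reaching 160/100. But from Cycle 3 the Schedule of Activities (Section 1.3) sets vital signs on Day 1 of each 21-day cycle, so an untreated participant can first be found above the higher threshold.

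**3. Does other text settle it?** Section 6.6.2 sends the reader to the hypertension subsection before Table 5. Footnote b and the stated aim lean towards continuing, but neither removes the withhold instruction. The France entry for this section in Appendix 7 changes only the entry BP.

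**4. Resume rule.** The pointer to what is described below reaches one restart rule, step 3 with its sub-bullets. Its BP condition (≤150 and ≤95 mm Hg, 48 hours) transfers easily. Its one-level reduction was written for persistence despite maximal therapy, and nothing says whether it applies to an earlier withhold. That reduction is 20 to 14 mg in Arm 1 (6/20 = 30%) and 24 to 20 mg in Arm 2 (4/24 = 16.7%).

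**5. Smallest dose effect.** Inputs: 21-day cycle; 20 mg (Arm 1) or 24 mg (Arm 2) daily; 48-hour minimum; a late dose may be taken within 12 hours (Sections 6.2.1 and 8.1.9.1.1). Assumptions: BP is controlled at 48 hours and the same dose is resumed. With k missed doses, the loss is k/21 of the cycle's dose.

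- Reading and antihypertensive start before the Day 1 dose: Days 1 and 2 are missed and dosing resumes on Day 3, so k = 2.
- Dose at 08:00 on Day 1, antihypertensive started at 13:00: Day 2 is missed. The 48 hours end at 13:00 on Day 3, when that day's dose is 5 hours late and still allowed, so k = 1.

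| | Full cycle | k = 1 | k = 2 |
|---|---|---|---|
| Arm 1 | 21 × 20 = 420 mg | 400 mg (−20 mg) | 380 mg (−40 mg) |
| Arm 2 | 21 × 24 = 504 mg | 480 mg (−24 mg) | 456 mg (−48 mg) |
| Loss | | 1/21 = 4.8% | 2/21 = 9.5% |

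Each further withheld day costs another 4.8%.

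**The case against.** The best defence is that the paragraph and the steps form an override and a default. The operative trigger in the withhold sentence is clinical, and BP is only an example of it. Footnote b and the stated aim fit that reading. The group in direct conflict is also narrow: participants on no antihypertensive who pass the 140/90 treatment threshold and reach 160/100 between checks. Interruptions are an ordinary part of lenvatinib dosing, and Section 6.6.2 requires Sponsor approval to resume only beyond 28 days.

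Much of this stands. Override and default is the likely intent, and the narrow scope lowers the severity. What does not stand is that the text says so: the same threshold is named alone in an 'or' list, and step 1 is unconditional for its group.

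A reader might infer three stronger points that the documents do not support.

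- *No resume dose is given.* There is a forward pointer, and it reaches a one-level reduction. What is unclear is whether that reduction applies. Table 5 also pairs interruption with a reduction for intolerable Grade 2 or Grade 3 toxicity.
- *Any participant with a cardiac or hemorrhage risk factor must be withheld at any BP.* The sentence concerns complications of uncontrolled hypertension and ends when BP is controlled, so it presupposes raised pressure.
- *A withhold costs at least two doses.* With the 12-hour allowance it can cost one.

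**Conclusion.** The concern holds as a contradiction in a safety-dosing rule. It is direct only for participants not yet on antihypertensives, and there is a related uncertainty over the dose after an early withhold. The minimum effect is about 1 to 2 missed doses per event, subject to the timing assumptions above. The possible one-level reduction is not counted in that size, because it arises only if step 3 is applied outside its stated condition. The documents do not say how often such readings occur, so no trial-level effect can be given.

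A reader might go on to question the response-rate analysis. Nothing here bears on ORR estimation, the sample size or the error rates. Severity is moderate: worth correcting because sites need one instruction, but not a threat to the trial's conclusions.

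**What to change.** Amend Section 6.6.2.1 as follows.

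1. Limit the withhold sentence to two cases: imminent risk of a hypertensive crisis, or confirmed systolic ≥160 or diastolic ≥100 mm Hg together with a significant risk factor for severe complications. Using systolic 'or' diastolic matches the trigger for the steps.
2. Add 'unless the withhold paragraph above applies' to the line that introduces steps 1 to 3.
3. Replace the undefined 'controlled' with systolic ≤150 and diastolic ≤95 mm Hg after at least 48 hours on the same antihypertensives.
4. State whether step 3's one-level reduction applies after such a withhold. Same dose or one level lower is the sponsor's clinical choice.

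The cost is a short wording change and a clarification to sites, with no change to the analysis or the sample size.

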6.6.2.2 Management of Proteinuria

Regular assessment of proteinuria should be conducted as detailed in the SoA (Section 1.3). Guidelines for assessment and management of proteinuria are as follows:

Detection and Confirmation

1. Perform urine dipstick testing or urinalysis per the SoA (Section 1.3). Urine dipstick testing is the preferred method for testing for urinary protein, however, urinalysis may be used if the use of urine dipsticks is not feasible.
2. A 24-hour urine collection initiated as soon as possible and at least within 72 hours (or an immediate spot urine protein-to-creatinine ratio [UPCR] test) is required in the following situations:
 - The first (initial) occurrence of $\geq 2+$ (≥ 100 mg/dL) proteinuria on urine dipstick (or urinalysis) while on study drug
 - A subsequent increase in severity of urine dipstick or urinalysis proteinuria occurring on the same lenvatinib dose level
 - When there has been a lenvatinib dose reduction and at the new dose level the urine protein dipstick result is $\geq 2+$ (≥ 100 mg/dL).
3. A 24-hour urine collection (initiated as soon as possible and at least within 72 hours) to verify the grade of proteinuria is required when UPCR is ≥ 2.4 .

Grading of Proteinuria:

- Grading according to NCI CTCAE v4.0 will be based on the 24-hour urinary protein result if one has been obtained. Management of lenvatinib administration will be based on the grade of proteinuria according to [Table 5](#).

Monitoring:

- Urine dipstick or urinalysis testing for participants with proteinuria $\geq 2+$ (≥ 100 mg/dL) should be performed on D15 (or more frequently as clinically indicated) until the results have been 1+ (30 mg/dL) or negative for 2 consecutive treatment cycles.
- Proteinuria monitoring can be performed at the local laboratory or investigator site but must be managed by the site physician.
- In the event of nephrotic syndrome, lenvatinib must be discontinued.

